### 7.3 Intermediate Follow-up

#### Follow-up 1 at 1-Month (Day 30 ± 2 weeks)

- Patients will complete their *Patient One-Month Follow-up Questionnaire* one-month post baseline independent of an in-office visit.

#### Follow-up 2 at 3-Months (Day 90 ± 2 weeks)

- Patients will complete their *Patient Three-Month Follow-up Questionnaire* three-month post baseline independent of an in-office visit.

### 7.4 Final Study Follow-up

#### Follow-up 3 at 6-Months (Day 180 ± 2 weeks)

- Patients will complete their *Patient Six-Month Follow-up Questionnaire* six-months post baseline independent of an in-office visit.

### 7.5 OMS and DA Data Collection

#### Middle of Enrollment Data Collection (when participating office has reached middle of patient enrollment)

- OMS completes mid-data collection *Doctor Questionnaire Regarding Use of Device*.
- DA completes mid-data collection *Dental Assistant Questionnaire Regarding Use of Device*.

## **End of Enrollment Data Collection (when participating office has completed patient enrollment)**

- OMS completes Doctor Questionnaire Regarding Use of Device at the end of patient enrollment.
- DA completes Assistant Questionnaire Regarding Use of Device at the end of patient enrollment.

### **7.6 Withdrawal From Study**

- Record date and reason for withdrawal.
- Consistent with Section 5.5.2, the only evaluations and data collection authorized will be information needed to address an unanticipated problem or other safety issue that may have led to his/her withdrawal from the study.

### **7.7 Unscheduled Visit**

For the purpose of the study, the patient does not need to see the surgeon after their 3rd molars are surgically removed. However, the patient may return to the OMS with concerns after surgical removal of their 3rd molars, including that they are having TMD pain. If the OMS determines that the concern is related only to 3rd molar removal, as described in their inter-office consent form for 3rd molar removal, then they will manage the patient for this. This includes the presence of TMD pain. If the OMS cannot determine if the concern is related to the study or believes it is related to the study, including use of the device, then they will inform the study coordinator who will discuss this event with the project PI. If they deem the event to be an adverse event related to the study, then it will be reported as described in Section 9.4.

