## 2.3 Potential Risks and Benefits

### 2.3.1 Potential Risks

There are potential risks of using the RJ2 device. If excessive force is placed on the device by the OMS, then the device could slide to a slightly different position. However, as soon as this force is stopped, then the device will stop moving. There is potential that the device could malfunction and lose pressure during the procedure. If this occurs, the passively controlled arms will fall away from the patient's jaw which could also compromise the support of the patient's jaw. To mitigate these risks, the dental assistant will be present behind the dental chair to support the jaw. Patients have similar

risk of jaw injury when their jaw is supported only by the dental assistant's hands since their hands can slip in position if excessive force is placed on the jaw, and their supporting arms and hands can become fatigued during procedures compromising their ability to support the jaw. In addition, patients could report that the padded jaw brace when placed under their jaw feels uncomfortable. If this occurs, then the dental assistant can reposition the brace to a position that is comfortable. There are no other anticipated safety risks to participating in this study beyond those risks inherent in 3rd molar extractions with moderate/deep sedation or general anesthesia. Patients do not receive 3rd molar extractions as a study procedure. Consequently, risks of 3rd molar extraction with moderate/deep sedation or general anesthesia will be discussed with the patient as part of normal clinical care and are not considered to be study-associated. Finally, if any adverse event (AE) occurs, then it will be documented and assessed by the study team.

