#### 9.1.2 *Adverse Events*

An AE is any untoward or unfavorable medical occurrence in a human subject, including any abnormal sign (for example, abnormal physical exam or laboratory finding), symptom, or disease, temporally associated with the subject’s participation in the research, whether or not considered related to the subject’s participation in the research.

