#### **9.5 Halting Rules**

For monitoring purposes, all AEs will be recorded throughout the trial, and the DCC will track all AEs, including all SAEs.

Decisions about stopping the trial will be made either by the investigators or by the NIDCR in consultation with the Medical Monitor. A formal stopping rule will use the group sequential method of Lan and DeMets, described in more detail in Section 12.3.2, applied separately to the two outcomes "Any AE" and "Any SAE", with P-values computed comparing the groups according to these outcomes using Fisher's exact test. As noted in 12.3.2 regarding efficacy, the exact sequential monitoring plan must be reviewed and approved by the NIDCR in consultation with the MMOR before any interim formal tests occur.

The investigators can stop enrollment in the study at any time based on the occurrence of an AE or UP that they deem of sufficient concern.

---

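### Section 7.7 has no AE recording step for complaints judged due only to the extraction; this conflicts with the duty to record all AEs and could let AE counts differ by arm

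*Combined protocol and SAP*

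**What the plan says.** Section 7.7 has two branches for a patient who comes back to the surgeon.

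- Concern judged due only to the extraction: "then they will manage the patient for this. This includes the presence of TMD pain". Nothing is said about recording it or telling the study.
- Concern unclear or attributed to the study: "If the OMS cannot determine if the concern is related to the study or believes it is related to the study", device use included, the surgeon informs the study coordinator, who takes it to the PI. A second judgement follows: "If they deem the event to be an adverse event related to the study, then it will be reported as described in Section 9.4".

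Section 2.3.1 points the same way. It says the risks of extraction under sedation or anesthesia are discussed "as part of normal clinical care and are not considered to be study-associated".

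The safety sections do not depend on attribution. Section 9.1.2 defines an AE "whether or not considered related to the subject"'s participation. Section 9.2 has the PI record all safety events from consent onward. Section 9.5 says "all AEs will be recorded throughout the trial" and that the DCC tracks them. Section 12.3.1 requires surgeons to record all AEs, and Section 16.1 gives the same duty to surgeons and their staff.

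Section 9.5 then specifies a stopping rule that compares the arms on Any AE and Any SAE by Fisher's exact test within a Lan-DeMets scheme. The exact monitoring plan must be approved before any formal interim test.

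**The concern.** Section 7.7 is the only place that describes what a surgeon does when a patient returns with a problem. A surgeon or coordinator working from it would reasonably conclude that an extraction-only complaint stays in the clinic. The PI and the DCC cannot record or track an event that nobody sends them.

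The sorting is done by someone who knows the allocation (Section 5.4.2), and only the experimental arm has a device to which a complaint can be attributed. The same jaw complaint could therefore reach the coordinator in one arm and stop at the surgeon in the other. More forwarding in experimental care could create an apparent excess of AEs with no true difference. If jaw complaints in that arm are put down to the extraction, a real device harm could be missed. TMD pain, the condition the device is meant to prevent, is placed by name in the managed branch.

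What is at stake is the AE counts behind the Section 9.5 rule and the Medical Monitor reports (Sections 10 and 16.4).

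**Working it through.** **1. The passages side by side**

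| Section | Who acts | Does it depend on attribution? |
|---|---|---|
| 7.7, extraction-only concern | Surgeon manages the patient | Yes; no recording step stated |
| 7.7, unclear or study-related concern | Surgeon informs coordinator, then PI | Yes; Section 9.4 reporting only if deemed related |
| 9.1.2 | Definition of an AE | No |
| 9.2 | PI records all safety events after consent | No |
| 9.5 | All AEs recorded; DCC tracks | No |
| 12.3.1 | Surgeons record all AEs | No |
| 16.1 | Surgeons and staff record AEs | No |

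Sections 12.3.1 and 16.1 address the same person as Section 7.7, and neither side refers to the other.

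**2. Is there a described backstop?** No visit after surgery is required (7.7). The listed content of the follow-up questionnaires is TMJ noise, jaw or temple pain, disability, modifying factors and course (8.1), with no general AE item. No AE form is named in Section 13, Section 16.3 or Appendix A. Site monitoring will not be conducted (11). The case report forms and the surgeons' manual are separate supplements that are not available here, so they may fill the gap.

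**3. Arm size.** The plan gives no AE rate or AE power figure. Its sample size serves only to set the arm size. For 14% against 28%, two-sided 0.05, 80% power, pooled variance:

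n = [1.960·√(2·0.21·0.79) + 0.842·√(0.14·0.86 + 0.28·0.72)]² / 0.14² = 131.7, so 132 per group.

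264 / 0.90 = 293.3, so 294 randomized, or 147 per arm. Both figures reproduce.

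**4. Illustration (the AE rate and the recorded shares are assumptions).** Let q be the true proportion of patients with an AE, equal in both arms, and let f be the share of those patients whose event reaches the study. Recorded counts are binomial(147, q·f) in each arm. The false-positive rate is the total probability of all pairs of counts with a two-sided Fisher p of 0.05 or less.

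| Share recorded, UC / EC | q = 10% | 20% | 30% | 40% |
|---|---|---|---|---|
| 100% / 100% | 3.3% | 3.6% | 3.7% | 3.7% |
| 50% / 50% | 2.4% | 3.3% | 3.4% | 3.6% |
| 50% / 75% | 9.2% | 20.5% | 32.7% | 45.8% |
| 25% / 50% | 11.6% | 29.1% | 47.1% | 62.1% |

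Under-recording alone does not inflate the error; a difference between arms does. The arms are equal in size, so reversing the shares gives the same rates in the opposite direction.

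Two single outcomes with q = 30% and expected counts rounded:
- 10% of UC and 30% of EC recorded: 147·0.30·0.10 = 4 and 147·0.30·0.30 = 13; p = 0.043.
- 10% of UC and 50% of EC recorded: 4 and 147·0.30·0.50 = 22; p = 0.0003.

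**5. The same outcomes at a half-way look.** With about 73 per arm the counts are 2 against 7 (p = 0.17) and 2 against 11 (p = 0.017). An O'Brien-Fleming-type boundary at half information lies at roughly 0.003 to 0.006. Neither outcome crosses it.

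**The case against.** The strongest reply is that Section 7.7 deals with clinical management and escalation and does not define the AE dataset. It never says that an extraction-only complaint goes unrecorded. Five other sections require recording whatever the cause, two of them addressed to the surgeon, and relatedness is graded separately in Section 9.3.1. This stands to the extent that non-recording is inferred from silence. It does not remove the conflict: Section 7.7 omits the recording step at the point where the surgeon needs it, and does not say whether TMD pain brought to the surgeon is an AE.

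A reader might go further and infer that AE counts must differ between arms as a built-in result of the procedure. The documents do not support that. Section 7.7 gives the same instruction in both arms and sends undetermined cases to the coordinator in either. A difference needs surgeons to attribute differently by arm, which is possible but not documented.

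A reader might also infer that a biased AE comparison is already planned. It is not. Sections 12.3 and 12.3.2 plan no interim analysis, Section 9.5 makes formal testing conditional on approval, and Section 12.4 lists no AE comparison.

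Finally, the illustration uses one 0.05 test on the full sample, when no enrollment would be left to halt, and not the Lan-DeMets boundary. That objection stands, as step 5 shows.

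**Conclusion.** The concern holds as an unreconciled conflict between Section 7.7 and Sections 9.1.2, 9.2, 9.5, 12.3.1 and 16.1. A site that follows Section 7.7 literally could record AEs differently by arm, because attribution is unblinded and only one arm has a device.

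Neither the size nor the direction of a bias can be computed from the documents. The false-positive rates of 9% to 62% and the single p-values only illustrate how sensitive an Any AE comparison would be to unequal recording. They rest on assumed AE rates and recorded shares and on a single full-sample test. With equal recording there is no inflation.

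The exposure is limited to the Section 9.5 rule, if it is ever activated, and to the six-monthly Medical Monitor reports. The primary outcome is not affected: TMD pain is taken from patient questionnaires in both arms, whatever the patient tells the surgeon. The point should be corrected, but it does not threaten the efficacy analysis.

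**What to change.** Reconcile Section 7.7 with the safety sections; no change to how patients are managed is needed.

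- State in Section 7.7 that every complaint brought to the surgeon that meets the Section 9.1.2 definition is recorded as an AE in both arms before attribution is considered, with relatedness as a separate field, and cross-refer to Sections 9.2, 9.5, 12.3.1 and 16.1.
- State whether TMD pain reported to the surgeon counts as an AE.
- Limit the coordinator and PI route in Section 7.7 to escalation and Section 9.4 reporting.
- State in Section 9.5 that any comparison of Any AE or Any SAE uses the set recorded without regard to attribution.
- Confirm that the case report forms and the surgeons' manual contain a matching AE form, and name it in Section 13, Section 16.3 and Appendix A.

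The cost is a few sentences of protocol wording, a short form if none exists, and modest extra data entry for complaints that surgeons already see.

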## 8 STUDY PROCEDURES /EVALUATIONS

### 8.1 Study Procedures/Evaluations

#### OMS and DAs – Training:

- The study coordinator will visit each OMS office, review the study protocol and *Manual for Surgeons and Dental Assistants* and demonstrate how to use the device. OMS will be consented, when required by their IRB, at the time of study training. For those dental assistants who are willing to participate, consent will be obtained by the study coordinator at the time of training.
- OMS and dental assistants will be formally and uniformly trained on site by the research coordinator in the dental office where the device will be employed prior to any procedure being performed by the OMS.

#### Patients – Baseline:

- Patients who have consented to study participation will provide contact information for study follow-up, demographic information and a baseline questionnaire, which will assess: 1) presence of any TMJ noise in past 3 months, 2) presence of any jaw or temple pain, 3) current pain or discomfort associated with their wisdom teeth, 3) Presence of any oral habits, and 4) and general health status.
- Patient will be randomized to: 1) Usual Care (UC) with a bite block and hand support of the jaw, or 2) Experimental Care (EC) with a bite block and the Restful Jaw device to support the jaw.
- The device will be positioned (EC group only) and placed prior to the surgical procedure.

#### OMS – Baseline:

- The OMS will complete the *Doctor Surgery Questionnaire* for each of the consented patients in both the EC and UC groups after the surgery is completed. The target is to have the OMS complete the questionnaire on the day of the surgery. This questionnaire assesses: 1) TMD pain present in the last 3 months, 2) any TMJ noise present, 3) information on surgical procedures (e.g., teeth extracted, eruption status, presence of pericoronitis or

infection, reason for extraction, procedure employed for removal, estimate of time to extract the tooth and sequence of extractions). In addition, if the device was used, OMS will record whether the use of the device was discontinued during the surgery.

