#### **5.4.2 *Masking Procedures***

In this RCT, it is not feasible to blind patients, surgeons, or dental assistants to treatment after the intervention assignments have occurred, so they will not be blinded. It is, however, feasible to mask the sequence of treatment assignments until the moment each assignment is made, and this will be done, as described in Section 5.4.1, above.

The DCC will also be un-blinded to treatment arm assignment. However, study staff and investigators will not have access to any interim outcome data. Unmasking procedures during the surgery will not be necessary as the patient, surgeon, and dental assistants will be un-blinded to the treatment group for each patient. The patient's record in the OMS office will include documentation of study participation and their group assignment (i.e., UC versus EC).

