#### Enrollment/Baseline Visit (Visit 1, Day 0)

- Verify, obtain and document consent from potential patient via electronic data capture consent form based on IRB requirements.
- Verify and document Health Insurance Portability and Accountability Act (HIPAA) authorization for use of the patient's Personal Health Information (PHI) in Research, based on IRB requirements.
- Patient completes patient contact information, patient demographics information, and *Baseline Patient Questionnaire*.
- Record results of TMD examination from OMS on *Doctor Surgery Questionnaire*.

- After a patient eligibility is confirmed and they have provided consent, the patient's random assignment to EC or UC is then automatically available to the OMS and their dental assistant on the tablet. The patient is then informed of their group assignment.
- OMS completes usual care extraction of 3rd molars with moderate/deep sedation or general anesthesia and bite block. If patient is randomized into the UC group, the procedure will be completed with a bite block and a DA holding the jaw. If patient is randomized into the EC group, the procedure will be completed with a bite block and the RJ2 device.
- OMS completes *Doctor Surgery Questionnaire*.

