- Baseline clinical findings by the surgeon (e.g., TMJ noise, eruption status, pericoronitis, soft-tissue infection, reason for extraction, difficulty of extraction, length and duration of the surgery, and pain or discomfort around third molars); see *Doctor Surgery Questionnaire*.
- Procedural characteristics, identified by the surgeon (e.g., type of extraction, amount of bone removal, use of grafting); see *Doctor Surgery Questionnaire*.

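### Sections 7.2 and 8.1 conflict on when the surgeon's pre-operative findings are recorded, so items treated as baseline adjusters may be entered after the arm is known

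*Combined protocol and SAP*

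**What the plan says.** Section 8.1 (OMS – Baseline) has the surgeon fill in the Doctor Surgery Questionnaire "for each of the consented patients in both the EC and UC groups after the surgery is completed". On timing it adds: "The target is to have the OMS complete the questionnaire on the day of the surgery". The first two items are "1) TMD pain present in the last 3 months, 2) any TMJ noise present", followed by surgical information that includes eruption status, pericoronitis or infection, and reason for extraction. The schedule overview in Section 4 also places this form after the extractions.

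Section 7.2 gives the Day 0 steps as a list. One step reads "Record results of TMD examination from OMS on" the Doctor Surgery Questionnaire. The next says that, once eligibility and consent are in place, "the patient's random assignment to EC or UC is then automatically available to the OMS and their dental assistant on the tablet". The extraction follows, and completion of the same questionnaire is the last step.

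Section 5.4.2 states that "it is not feasible to blind patients, surgeons, or dental assistants to treatment after the intervention assignments have occurred".

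Section 12.4 groups the form's content as "Baseline clinical findings by the surgeon" in its list of potential adjusters. The adjusted version of the primary analysis draws from that list the characteristics that differ materially between the arms.

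**The concern.** A baseline covariate should be fixed before the arm is known. Several surgeon items describe the patient before surgery, but the only form that carries them is described as completed after surgery by someone who knows the arm and how the operation went. If that knowledge colours what is written, for example whether joint noise or pericoronitis is noted, the item becomes partly a consequence of assignment.

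The adjuster rule makes this worse. A characteristic enters the adjusted model because it differs by arm, and an item recorded differently by arm will tend to meet that condition. The adjusted analysis is meant to check that randomization balanced the arms, so it should not rest on data that may have been written after unblinding.

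Late entry might also go unnoticed. Section 11 plans no site monitoring, and the example of a data check in Section 14 concerns whether entries are present and valid, not when they were made relative to assignment.

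**Working it through.** The point is about timing, and the plan gives no figure to reproduce. The check sets the sections side by side.

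**Step 1: when the form is completed.** Section 4, the last Day 0 step of Section 7.2, and Section 8.1 all say after surgery. One earlier step in Section 7.2 implies that part of it is written before assignment. No section describes a two-part form, a time stamp or a lock. Appendix A has a single row for a Doctor Baseline Questionnaire, a name that does not appear in the form lists of Sections 13 and 16.3, so it does not settle the question.

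**Step 2: item by item.**

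| Surgeon item | Listed for the form in 8.1 | Recording step before assignment in 7.2 | Named among surgeon findings in 12.4 |
|---|---|---|---|
| TMD pain, last 3 months | Yes | Possibly, if part of the TMD examination | No (the list is of examples) |
| TMJ noise | Yes | Possibly, if part of the TMD examination | Yes |
| Eruption status | Yes | None | Yes |
| Pericoronitis or infection | Yes | None | Yes |
| Reason for extraction | Yes | None | Yes |
| Pain around third molars | Not listed | None | Yes |
| Difficulty and duration of surgery | Time estimate only | Cannot exist yet | Yes |

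For the TMD items the sections conflict. For eruption status, pericoronitis or infection, reason for extraction and third-molar pain there is no conflict, because no pre-assignment step exists.

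**Step 3: where the items are used.** Section 12.4 uses potential adjusters in three stated places: the comparison of baseline characteristics, the adjusted check of the primary analysis, and the adjusted analysis of characteristic pain intensity. The primary analysis itself has no adjusters.

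**Step 4: how a distortion would arise.** Take pain intensity with an identity link (an assumption; the link is not stated). Let Δ be a difference between arms in the recorded item that comes only from how it was recorded, and γ the slope of the outcome on the recorded item within arm. Then approximately

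adjusted difference − unadjusted difference = −γ × Δ.

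With a true chance imbalance, this term is a useful correction. With a recording artefact, it is an error. The documents give neither γ nor Δ, nor a prevalence of TMJ noise in this population, so the term cannot be evaluated.

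**The case against.** The strongest reply is that the Section 7.2 steps read as a sequence: the TMD examination is recorded, the arm is released, the surgery is done, and the form is finished. On that reading the form is begun before assignment and completed afterwards, and Section 8.1 describes only its completion. Appendix A shows an oral exam at baseline, Section 13 has offices keep records, and the case report forms and surgeon manual are supplemental materials that may already divide the form. This stands in part. Late entry of the TMD items is not established, and a reader who infers that the surgeon writes them from memory goes beyond the text. The reply does not cover the items with no pre-assignment step, and it supplies no lock.

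A reader might also infer that an exclusion criterion first reaches the study record after randomization. The documents do not support this. Section 5.2 defines the exclusion by what the patient reports. Sections 4 and 7.1 settle eligibility on the Screening Questionnaire, and Section 5.4.1 gives the assignment only after eligibility is confirmed. The patient's own questionnaire, which also asks about jaw or temple pain, is completed before surgery. The surgeon's item repeats this information; it is not the source. One narrow route remains: Section 5.5.1 lets an investigator end participation for an exclusion not recognized earlier, yet also limits withdrawal to patients who no longer consent to give data. Those two statements need reconciling in their own right.

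Finally, the consequence is modest. The primary outcome is patient-reported, its analysis is unadjusted, and patient-reported TMJ noise and wisdom-tooth pain are already candidate adjusters collected before surgery. This stands, and it bounds the point. Patient report does not, however, replace the surgeon's assessment of eruption status, pericoronitis or reason for extraction.

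**Conclusion.** The concern holds as an unresolved conflict over the TMD items and a gap for the other pre-operative surgeon items. It affects supporting analyses only: the baseline comparison, the adjusted check and the adjusted pain-intensity analysis. It does not alter the unadjusted primary estimate or the determination of eligibility.

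Its size cannot be stated. Any percentage for spurious imbalance would need an assumed prevalence and an assumed degree of one-sided recording, and the documents support neither. Such a figure would also describe how often a baseline test is significant, not bias in the treatment effect, and the adjuster rule is not expressed as a significance test.

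The conclusion assumes that the form is not already split and locked in the case report forms. If it is, only the protocol wording needs correcting. The point is worth acting on because the remedy is cheap.

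**What to change.** Reconcile Sections 7.2 and 8.1 along these lines:

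- The surgeon's pre-operative items (TMD pain history, TMJ noise, eruption status, pericoronitis or infection, reason for extraction, third-molar pain) are entered and locked in the electronic data capture system before the tablet releases the assignment.
- Procedural items, surgical time and device discontinuation are completed after surgery, as now.
- Section 12.4 admits as baseline adjusters only the locked surgeon items and patient-reported baseline data. Difficulty and duration of surgery and the procedural characteristics then leave the baseline adjuster list and can be reported descriptively.
- Appendix A uses the same form name and shows the two entry times.

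The tablet already controls release of the assignment (Section 5.4.1), and the data capture system already stops users who leave required entries missing (Section 16.2). The cost is therefore a small system change and a minute or two of surgeon time before surgery.
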